4.2.2. Exclusion Criteria

- Age  $< 18$  years
- Presence of urinary fistula
- Male genital anatomy
- Undergoing evaluation or treatment of recurrent (2 or more infections in the last 6 months or 3 or more infections in the last 12 months) or current urinary tract infection
- Current Bladder stones
- Bladder cancer or suspected bladder cancer
- Gross Hematuria
- Pregnancy or planning to become pregnant during the study
- Cognitive impairment
- Central or peripheral neurologic disorders such as multiple sclerosis, Parkinson's disease, spina bifida, spinal cord lesions, etc.
- Metal implants such as pacemaker, implantable defibrillator, or metal implants where PTNS or TENS device needs to be placed (ankle/leg)
- Uncontrolled diabetes
- Diabetes with peripheral nerve involvement

PROTOCOL TITLE: INTENSE: INvestigation of TENS Efficacy versus Posterior Tibial Nerve Stimulation for overactive bladder

- Current use of anticoagulants (excluding aspirin)
- Current use of anticholinergics or use within the last 4 weeks
- Current use of botox bladder injections or bladder botox injection within the last year (12 months)
- Current use of sacral neuromodulation therapy or currently implanted sacral neuromodulation device or leads
- Bladder outlet obstruction
- Urinary retention or gastric retention
- Painful Bladder Syndrome/Interstitial Cystitis
- Unable to be contacted for follow up by telephone
- Inability to speak/read/understand English or Spanish

4.3. We have decided to only include adults (age  $\geq 18$  years) who are capable of giving informed consent. Children, pregnant women and prisoners will be excluded.

4.4. We will include English and Spanish speaking populations only, as our primary outcome measures have not been validated in other languages. We are excluding men as we are a Urogynecology practice and therefore do not treat that population.

4.4.1. Because we are excluding pregnant women, during participant recruitment women will be asked if they are pregnant or have plans to become pregnant in the next 3 months. Their sexual activity, menopause status and surgical history (specifically hysterectomy or tubal ligation) will also be determined, which are standard questions asked in our practice for new patients. If there is concern for pregnancy, we will perform a urine pregnancy test of the participant on the day of enrollment.

## 5. Number of Subjects

5.1. This is a single-center study at the University of New Mexico, therefore the total number of subjects at the University of New Mexico is the total number of subjects for the study.

5.2. The total number of subjects to be recruited at this site is up to 130 patients.

5.3. *Sample size calculation:* The primary outcome for this study is the change in the OAB-q total score from baseline to 3 months. We used the means and standard deviation for this questionnaire from an unpublished pilot RCT study from Walter Reed that compares PTNS and TENS for the treatment of OAB (unpublished work). We have powered the study based on a 10-point difference as significant between groups. This 10-point difference used for the power calculation is based on the previously established minimum important difference. To achieve power for this non-inferiority RCT study showing that the difference between groups is less than 10 points, we need 40 patients per group (80 total) to detect no difference with  $\alpha = 0.05$  and 80% power. Allowing for dropout of up to 30%, we will aim to randomize 114 patients, and will plan to recruit up to 130 to allow for potentially higher drop-out, as the study primary outcome is at the 12 weeks' time point. As we plan to perform both per-protocol and intention-to-treat analysis, the sample size must be met for both per-protocol and intention-to-treat analysis, with the per-protocol patients (those in the PTNS group completing at 12 treatments in a total of 13 weeks) being expected to be a lower sample size.

## 6. Study Timelines

6.1. Based on the current clinic volume in the UNM division of Urogynecology, we estimate recruitment up to 130 patients will be feasible over 2 years. A review of our clinic calendar revealed in 1 months' time, the urogynecology division typically sees 10-20 patients who would meet criteria for our study. Assuming 25% enrollment (due to time commitment and eligibility criteria), we will be able to recruit our projected number of patients in less than 2 years. Participants will be followed for 3 months after randomization, so we expect an additional 3 months will be needed to collect follow up data. We estimate that data analysis and composition of the manuscript will take an additional 6 months.

## 7. Study Endpoints:

- 7.1. The **primary endpoint** of our study is to determine the change in OAB-q score in patients who undergo 12 weeks of PTNS compared to those who undergo TENS therapy for OAB. Our secondary endpoints include change in OAB-q Symptom Bother subscale score from baseline, change in OAB-q HRQL subscale score from baseline, number or urinary incontinence episodes, number of voids per day, number of voids per night, patient satisfaction question (PSQ) and patient compliance.
- 7.2. Due to the extremely low risk of the therapeutic interventions, we do not have any **safety endpoints**.
- 7.3. Our **exploratory endpoints** are to investigate compliance with treatment between groups and preference between therapeutic options.

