## 1. Objectives

- 1.1. The objective of this research is to perform a non-masked, non-inferiority randomized controlled trial to assess the quality of life (QOL) of women with idiopathic overactive bladder (OAB) before and after treatment with percutaneous tibial nerve stimulation (PTNS) or transcutaneous electrical nerve stimulation (TENS) of tibial nerve. The target population is patients with OAB who previously failed first- and second-line treatments and desire non-surgical management.
- 1.2. Our central hypothesis is that a TENS unit is non-inferior to PTNS for improving the quality of life and symptom distress of women with OAB. The specific aims are:
  - 1.2.1. To compare the effects on health-related quality of life (HRQoL) and symptom bother as measured by the change in score from baseline of the Overactive Bladder questionnaire (OAB-q) in women with urgency urinary incontinence or overactive bladder before and after PTNS versus TENS after 3 months of therapy. Secondary outcomes related to this aim include change in symptom bother alone, as measured by the OAB-q symptom subscale and change in HRQL alone, as measured by the OAB-q HRQL subscale from baseline. **Hypothesis:** TENS will demonstrate similar effects on symptoms and symptom-associated HRQoL in the treatment of women with OAB compared to PTNS.
  - 1.2.2. To compare the rates of treatment success, as defined as 50% or more reduction of urinary incontinence episodes or 25% or more reduction in day or night voids in women with OAB before and after PTNS versus TENS after 3 months of therapy. The number of urinary incontinence episodes, number of voids per day and number of voids per night will be measured by a three-day voiding diary. **Hypothesis:** TENS will demonstrate similar rates of treatment success in women with OAB compared to PTNS.
  - 1.2.3. To perform a comparative analysis of patient satisfaction and compliance between TENS and PTNS. Patient satisfaction will be measured by a patient satisfaction question (PSQ). Patient compliance will be measured by number of treatment sessions completed as verified by clinical records of completed PTNS treatments and TENS device interrogation. **Hypothesis:** Women will be satisfied with both TENS and PTNS treatment and will have greater treatment compliance with TENS compared to PTNS.

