### 13.Data Analysis

- 13.1. *Data Analysis:* Between and within group differences will be evaluated using Fisher's exact test for categorical variables and t-tests for continuous variables, as we expect the data will be normally distributed. Wilcoxon rank-sum test will be used for continuous variables that are not normally distributed. If there are any baseline differences between groups, a multivariate analysis will determine the contribution of these differences to observed differences (if any) between groups.
- 13.2. *Intention-to-treat analysis:* We plan to perform the primary analysis as "intention-to-treat" indicating that patients will be analyzed in the group to which they were randomized, regardless of compliance with study procedures, unless they asked to be withdrawn or were withdrawn by investigators due to safety or validity concerns. For example, PTNS patients that miss more than one session or do not make up a missed session of their office PTNS would still be analyzed in the "intention-to-treat" analysis as being in the PTNS group.
- 13.3. *Per protocol analysis:* We plan to perform a secondary analysis as "per protocol" indicating that patients will be analyzed in the group to which they were randomized only if they complete a full 12 weeks of treatment in compliance with study procedures, meaning that women assigned to the PTNS arm completed 12 weekly PTNS sessions in the office in 13 weeks or less, and women in the at-home TENS arm performed TENS stimulation at least 5 days per week for 12 weeks, as averaged over 12 weeks. For example, PTNS patients that miss more than one session or do not make up a missed session of their office PTNS will not be analyzed in the "per protocol" analysis as being in the PTNS group.
- 13.4. *Power Analysis:* Power analysis was performed based on previously reported means and standard deviation for the OAB-q. The primary outcome of this study is improvement in HRQL and symptom bother of OAB/UUI as measured by the OAB-q. We used the means and standard deviation for this questionnaire from a prior unpublished pilot RCT from Walter Reed comparing PTNS and TENS for the treatment of OAB. We have assumed a change score of greater than 10 points to be significant between groups based on the minimally important difference that has been previously established. To achieve significance for a non-inferiority study using these assumptions we would need 80 patients,

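### Aim 1.2.2 compares treatment-success rates, but section 7.1 omits treatment success and lists three diary counts with no time point or change from baseline, and no rule says which result answers the aim

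*Combined protocol and SAP*

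**What the plan says.** Section 1.2.2 sets the second aim as a comparison of "treatment success, as defined as 50% or more reduction of urinary incontinence episodes or 25% or more reduction in day or night voids" after 3 months of therapy. Its hypothesis is about the same quantity: "TENS will demonstrate similar rates of treatment success in women with OAB compared to PTNS". The counts enter that aim as what the diary records: the incontinence episodes, "number of voids per day and number of voids per night will be measured by a three-day voiding diary".

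Section 7.1 opens its list with "Our secondary endpoints include change in OAB-q Symptom Bother subscale score from baseline" and continues with "change in OAB-q HRQL subscale score from baseline". It then gives "number or urinary incontinence episodes, number of voids per day, number of voids per night, patient satisfaction question (PSQ) and patient compliance". Treatment success is not there. Both OAB-q subscales are written as changes from baseline; the diary items are not, and they carry no time point.

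Section 13.1 assigns tests by variable type: "Fisher's exact test for categorical variables and t-tests for continuous variables", with the Wilcoxon rank-sum test for continuous variables that are not normal. It adds a multivariate analysis if baseline differences between the groups appear. Neither 12.2 nor section 13 names treatment success. Table 1 collects the diary at baseline, 6 weeks and 12 weeks.

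**The concern.** The only outcome named in the hypothesis of aim 1.2.2 is missing from the section that lists the endpoints. What stands there instead is three separate counts of a different form. An analyst who starts from 1.2.2 runs one comparison of proportions; one who starts from 7.1 runs three comparisons of counts. Both could claim to follow the plan.

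The trial is unmasked (section 3) and the diary is completed by the patient, so the choice between these routes could be made after the results are known. A second consequence concerns precision. The baseline diary is collected, but whether it enters the between-arm comparison of the counts depends on whether someone judges the arms to differ at baseline. That is a data-dependent decision, and it gives up precision the trial could have at no cost.

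**Working it through.** **1. The two sections side by side.**

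| | Section 1.2.2 | Section 7.1 |
|---|---|---|
| Diary outcome | one binary composite | three counts |
| Relation to baseline | percentage reduction | not stated |
| Time point | 3 months | not stated |
| Test implied by 13.1 | Fisher's exact | t-test or Wilcoxon, one per count |
| Baseline adjustment | built into the definition | only if baseline differences are seen |

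The tests are inferred from 13.1; section 7.1 assigns none.

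**2. Inputs for the size of the problem.** From the documents: 40 women per arm (section 5.3, sized on the OAB-q only) and alpha 0.05, taken here as two-sided because the sidedness is not stated. The plan gives no rate, margin or power for any diary outcome, so there is no figure of its own to reproduce.

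Assumed: each woman's leak rate is gamma (shape 1.5, mean 3) plus 0.3, so the mean is 3 + 0.3 = 3.3 per day. Three-day counts are Poisson. The individual response is log-normal with SD 0.6. Success here means at least 50% fewer leaks, which is one component of the composite. There were 3000 simulated trials per scenario.

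**3. How often Fisher's test on leak success and the t-test on the raw week-12 leak count differ in significance** (ranges are over repeated runs).

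| Mean leak reduction | Disagreement |
|---|---|
| 40% vs 40% | 6-7% |
| 50% vs 40% | 14% |
| 60% vs 30% | 32-37% |
| 60% vs 20% | 28-29% |
| 60% vs 10% | 16-18% |

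Using the rank-sum test instead of the t-test leaves this at about 7% with equal arms and about one trial in three at 60% vs 30%.

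**4. Value of the baseline covariate.** At 60% vs 30%, power is 54% for the raw count, 53% for Fisher's test on leak success, and 73% for the count adjusted for its baseline value. With equal arms the adjusted analysis rejects in 4.9% of trials. The SE of the arm difference is 0.50 leaks per day unadjusted and 0.41 adjusted:

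1 - 0.41/0.50 = 0.18.

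In sample-size terms, (0.41/0.50)² = 0.67, so 40 women per arm with adjustment are as precise as about 40/0.67 = 60 without it.

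**5. Side check on the full composite, under different assumed inputs.** Three-day baseline means were 9 leaks, 27 day voids and 6 night voids, with typical reductions of 50%/15%/20% in one arm. Fisher's test on composite success and the t-test on any single count differ in:
- about 7% of trials with equal arms;
- 10-16% with 40%/12%/15% in the other arm;
- 21-33% with 30%/8%/10%;
- 37-49% with 10%/3%/5%.

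The pattern is the same: little disagreement when the arms are alike, more when they differ.

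**The case against.** The strongest reply is that 7.1 and 1.2.2 do not compete. Section 7.1 uses the word include, so its list is not closed. Its three diary items are the variables that 1.2.2 feeds into the success rule, and the hypothesis in 1.2.2 already names the deciding comparison. On that reading the defect is a missing cross-reference. This stands in part: 7.1 does not prescribe a rival test, and the plan's intent can be guessed. It does not remove the gap, because the item left out is the one the aim turns on and the counts are listed as endpoints in their own right.

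A reader might infer that the two analyses often disagree. The documents say nothing on this. Under the trial's own hypothesis of similar arms the simulated figure is about 7%; the 30-37% assumes that one arm's reduction is twice the other's. It also reflects low power. Two independent tests with power 54% and 53% would disagree in 0.54 × 0.47 + 0.46 × 0.53 = 50% of trials.

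A reader might also infer that the plan ignores the baseline diary, so that chance imbalance goes uncorrected. Section 13.1 does not support that: it plans within-group comparisons, and a multivariate analysis if baseline differences are found. That provision is weaker than a prespecified covariate, but it exists.

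Finally, the simulation scores significance, and a non-significant difference does not show that the arms are similar. That is fair, and is a reason to report intervals. These are also secondary endpoints on which the trial was not sized.

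**Conclusion.** The point holds as an inconsistency between the aim and the endpoint list. Aim 1.2.2 is about treatment-success rates, 7.1 leaves that endpoint out and lists counts of unstated form and timing, and no rule links them. The two forms can lead to different conclusions; that they often do is not established.

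The sizes are about 7% disagreement with equal arms and about 30-37% at 60% vs 30%, with an SE reduction of roughly 18% from a baseline covariate. All of these rest on assumed leak rates, spread and response. The disagreement figures use leak success rather than the composite, for which only a side check under other assumed inputs is available. The inconsistency itself rests on the text alone. It should be corrected, ideally before outcome data are seen; it does not touch the primary endpoint.

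**What to change.** In 7.1, add treatment success at 12 weeks, as defined in 1.2.2, and state that it is the endpoint that answers aim 1.2.2. Report it as the TENS minus PTNS difference in proportions with a 95% CI, alongside Fisher's test.

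Give the three diary counts a time point (12 weeks) and a unit (per diary day). In 13.1, specify that each count is analysed with its own baseline count as a prespecified covariate and reported as an adjusted arm difference with a 95% CI. For these outcomes this replaces both the unadjusted test and the adjustment that depends on seeing baseline differences.

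The cost is protocol and analysis wording. Table 1 already collects the diary at both time points, so no visit, form or participant is added. The one trade-off is that the counts can no longer serve as an alternative answer to aim 1.2.2.

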## 8. Research Setting

- 8.1. The study will be performed at the University of New Mexico (UNM) Eubank Women's Primary Care Clinic and Sandoval Regional Medical Center (SRMC) Urogynecology clinics. These Urogynecology clinics are dedicated to care of women with pelvic floor disorders such OAB, the target population for this study.
- 8.2. Potential subjects will be recruited in the UNM Eubank and SRMC clinics when they present for care for OAB/UII, either in person or virtually via telephone or Zoom care visits. All patients will have a history and physical taken to determine their study eligibility. Recruitment will take place either in private exam rooms at these clinics or over HIPAA-compliant telephone or Zoom conversation. After recruitment, they will undergo the informed consent via the same means as recruitment and complete initial questionnaires in clinic or will be sent a copy (digital or mail) to complete if enrolled virtually. Patients in the TENS group will be given their TENS device in clinic and research staff will assist in educating participants on proper placement and use of the device, as well as provide a standardized treatment protocol they will complete at home. The patients randomized to PTNS will have their sessions at the UNM Eubank Women's Primary Care Clinic.
- 8.3. There are no other laboratory tests in this trial beyond what would routinely be collected in the work up of OAB.
- 8.4. There will not be involvement of any community advisory board.
- 8.5. There will not be any research conducted outside of the UNM HSC and its affiliates.

## 9. Resources Available

- 9.1. Qualifications of PI and study staff: [name] is a board-certified subspecialist in Urogynecology and will serve as the primary investigator (PI) for this study. She is an experienced researcher at UNM and eligible PI at UNM, in addition to serving on an HRRC at the UNM HSC Institutional Review Board, which makes her familiar with ethical and compliant practices. She has been the PI on multiple research trials and has successfully completed randomized control trials both as a fellow and now as faculty at UNM. [name], a co-investigator on this project, is a board-certified in Obstetrics and Gynecology and is board-eligible for Urogynecology, as she recently completed her fellowship. She is an experienced researcher who has completed multiple research projects in Urogynecology, including a randomized control trial, as a resident and fellow. She recently joined as faculty at UNM. [name], a co-investigator on this project, is the fellow who has a total of 12 months of protected research time during her fellowship in order to complete this study.
- 9.2. This trial does not require any medical decision-making or ordering of therapeutics due to research protocols.
- 9.3. Resources available to conduct the research: The University of New Mexico (UNM) Urogynecology division operates at two main locations. UNM Eubank Urogynecology Clinic, located in Northeast Albuquerque, provides a full range of services for women with pelvic floor disorders. The Eubank clinic consists of 8 examination rooms, 2 treatment rooms, and 2 physical therapy rooms. Our second location is at Sandoval Regional Medical Center (SRMC), a community-based facility located in Rio Rancho, New Mexico, a large suburb located outside of Albuquerque.

**Research Staff:** The Urogynecology Division employs a clinical research specialist as well as research coordinators. Our research staff has extensive experience conducting multi-center investigations and recruiting patients to clinical studies, with special expertise in community-based research and quality of life studies.

**Research Experience:** The Urogynecology Division at UNM has a strong history of conducting high quality research and collaboration with other investigators in the US and abroad, and has consistently met or exceeded recruitment goals on time. We have been members of the NICHD-sponsored Pelvic Floor Disorders Network (PFDN), and have met recruitment goals with high rates of follow-up and accurate data collection. In addition to PFDN research, [name] has mentored and has been the PI on multiple clinical trials and contributes multiple publications in peer-reviewed journals. Her Curriculum Vitae is attached.

Our group is well versed in the importance of adherence to protocols, timely completion of regulatory requirements, effective recruitment strategies, and the importance of the inclusion of minority subjects. Research is integral to all aspects of Divisional work; importantly, all members of the clinical team participate in research efforts. There are weekly research meetings to discuss the progress of the ongoing studies within the department, and it is an excellent forum to ensure that all involved are adequately informed of their duties, of the protocol, and of the procedures.

PROTOCOL TITLE: INTENSE: INvestigation of TENS Efficacy versus Posterior Tibial Nerve Stimulation for overactive bladder

We do not anticipate that emergency care will be needed for this study, as the interventions are low-risk. However, the urogynecology physicians are available on a 24 hour basis, 7 days per week for their patients requiring emergency care for any reason, including those relating to study participation.

